**13.6 Withdrawal from Study Participation:**

Explain the process for withdrawal and specify whether or not the subjects will be given the opportunity to withdraw their data their data/specimens in the event they wish to withdraw from the study

Participants may withdraw at any time by calling or emailing the study team. The study phone number and email are provided on the informed consent form. Participants will not have the opportunity to withdraw their data at any point in the study. Study withdrawal will not impact participant medical care or status in the military.

**14.0 Risks and Benefits**

**14.1 Risks of Harm:**

Identify all research-related risks of harm to which the subject will be exposed for each research procedure or intervention as a result of participation in this study. Consider the risks of breach of confidentiality, psychological, legal, social, and economic risks as well as physical risks. Do not describe risks from standard care procedures; only describe risks from procedures done for research purposes

Side effects of NAC are uncommon and relatively minor. The most frequently reported side effects are nausea, vomiting, and diarrhea. They often occur at identical rates to placebo. Rarely and primarily with intravenous administration, anaphylactic reactions may occur and can consist of rash, pruritus, angioedema, bronchospasm, tachycardia, and blood pressure dysregulation. Finally, given the limited reports on NAC in pregnant and lactating women, it should not be used in this population in the context of research and thus this is an exclusion criteria.

Sources: 1) FDA approved acetylcysteine labels (<https://dailymed.nlm.nih.gov/dailymed/index.cfm>)

Data collection may risk loss of privacy.

There is a risk of alcohol withdrawal.

There are legal risks if the participant enters the base intoxicated and/or the NSAB police are called.

There is a chance that participants could experience side effects such as nausea, motion sickness, eye strain, or seizures while completing the virtual reality-based assessment. Symptoms of virtual reality exposure can persist and become more apparent hours after use. These symptoms may put participants at an increased risk of injury when engaging in normal activities such as driving, operating machinery, or engaging in other demanding activities.

For military personnel, there is a risk that their command could be informed of their intoxication by the emergency department if the participant is transported there for alcohol withdrawal.

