Participants with a BAC of 0 will complete the informed consent process. They will undergo a physical exam by the physician. During the physical, female participants will undergo a pregnancy screen using a pregnancy test kit. If the screen is positive, they will be told they are not eligible to participate and they will not be counted in the study's enrollment number. Further, they will be instructed to contact their primary care provider to confirm the results and discuss the risks of alcohol use during pregnancy. Next, the RA will conduct the MADRS interview, then participants will complete the TLFB self-report form. They will then complete the computer questionnaires (demographics, ASSIST, AUDIT, APT, PACS, DDT, SIAS-6, SPS-6, e-cigarette questions, HONC, GAD-7, mental health services, medications and supplements, and military service questions) and behavioral tasks (Stop Signal, N-back, and Trail Making). Participants will be asked the treatment questions and referred to mental health resources by the RA. They will then be scheduled for their next study session and complete payment paperwork with the RA. Then they will be randomized to either 7 weeks of oral NAC (3000 milligrams) or 7 weeks of placebo. We will advise participants to inform their provider of participating in this research study and of taking 3000mg NAC or placebo. Participants will be given a business card to give to their provider stating they are in the study and taking 3000mg of NAC or placebo. Participants will be instructed to go to the Investigational Pharmacy (building 9) immediately after their appointment to pick up their study medication. They will be escorted by the RA if they have never been before or don't remember how to get there. The pharmacy will handle gender stratified randomization. The first study session will take approximately 3 hrs to complete.

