#### 12.6 Exclusion Criteria:

Order Number	Criteria
1	Lifetime clinical diagnosis of schizophrenia or bipolar disorder
2	Currently receiving medication for the treatment of alcohol use disorder including oral or injectable naltrexone (ReVia, Vivitrol), disulfiram (Antabuse), and acamprosate (Campral).
3	Pregnancy
4	Lack of English fluency sufficient to complete study measures.
5	Trying to get pregnant in the next 4 months.
6	Hospitalized because of alcohol use in the past 12 months.
7	History of seizures or delirium tremens.
8	History of liver disease
9	Diagnosis of a neurocognitive disorder (e.g., dementia, alzheimer's, intellectual disability).
10	Individuals who were never enrolled into ATS.

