#### 13.3 Please describe the pre-screening process. If no pre-screening, enter Not Applicable in the text editor

Participants will complete a brief phone screen in which they will be asked the following eligibility criteria questions:

1. *Have you used any drugs other than marijuana in the past 30 days?*  
*If yes: Which drugs?*
2. *Have you ever had a seizure?*
3. *Have you ever had delirium tremens or DT?*
4. *Have you been to the hospital because of alcohol use in the past 12 months?*
5. *Have you ever been diagnosed with schizophrenia?*
6. *Have you ever been diagnosed with bipolar disorder?*
7. *Have you ever been diagnosed with a neurocognitive disorder such as dementia or Alzheimer's?*
8. *Have you ever been diagnosed with an intellectual disability such as mental retardation? (NOTE: ADHD is ok)*
9. *Do you have any chronic medical conditions associated with alcohol use (such as liver disease)?*
10. *Are you currently receiving medication for the treatment of alcohol use disorder? If so, what medication are you taking? [Exclude if taking oral or injectable naltrexone (ReVia, Vivitrol), disulfiram (Antabuse), and acamprosate (Campral)]*
11. *Female only: Are you pregnant or trying to get pregnant sometime in the next 4 months?*
12. *How old are you?*

SCID-5 AUD module

If they meet eligibility criteria, they will be scheduled for their baseline visit. They will be told that they need to be abstinent from alcohol for at least 24 hours before their baseline appointment and that they will be breathalyzed to confirm a BAC of 0.

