**Methods and Frequency of Analysis:**

Data acquisition will be ensured during each session using checklist "flowsheets" (attached to the protocol). The PI will review the full collection of data at least monthly. All data will be stored in locked filing cabinets, secure USU computers, and deidentified data on secure google drive folders.

A study physician will conduct physical exams prior to enrollment and will monitor participants for side effects. Participants will be asked about adverse events weekly by the study physician. Participants may withdraw from the study at any time by contacting the research team, as stated in the consent form. The principal investigator may terminate any individuals' participation in the study at any time if he determines this to be in their best interest, if they are unable to comply with the procedures required, or if they no longer meet eligibility criteria.

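### No written eligibility rule covers a known previous allergic reaction to acetylcysteine, although the protocol names anaphylaxis as a rare risk of the drug

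*Combined protocol and SAP*

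**What the plan says.** Section 14.1 (Risks of Harm) describes side effects as uncommon and mostly gastrointestinal, then adds: "Rarely and primarily with intravenous administration, anaphylactic reactions may occur and can consist of rash, pruritus, angioedema, bronchospasm, tachycardia, and blood pressure dysregulation". Section 16.1 repeats this under expected adverse events.

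Eligibility is set by three inclusion criteria (12.5) and ten exclusion criteria (12.6). It is first checked by a phone screen of twelve questions plus the alcohol use disorder module of the diagnostic interview (13.3).

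At the baseline visit (10.1), after consent and before randomization, "They will undergo a physical exam by the physician". The monitoring plan in 15.1 confirms the timing: "A study physician will conduct physical exams prior to enrollment and will monitor participants for side effects". The baseline questionnaire on medications and supplements (10.2) records each product and why it is taken.

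In 18.2 the drug is oral, 1500 mg twice daily. The field for contraindications and interactions contains only a pointer to 14.1 and 16.1. The same table names the investigators who may prescribe.

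**The concern.** When a protocol names a serious reaction to its drug, one expects a line on people who already know that they had it. Here there is none. A candidate with such a history can answer every listed question truthfully and still qualify.

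What is at stake is the safety of a rare individual. Participants collect capsules from the pharmacy after the visit and take them at home. No observed first dose is described, and the next scheduled contact is the Week 1 visit. Screening is thus the easiest point at which to act on a known history. Earlier exposure is plausible, because section 9.2 says that NAC is sold over the counter and is an approved antidote for acetaminophen overdose.

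There is also a small operational stake. Section 16.1 gives allergic bronchospasm needing intensive treatment as an example of a serious adverse event, and a single serious event judged potentially related pauses the protocol.

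**Working it through.** The plan states no figure on this point and none can be derived, so the check is a reading of every place where a rule could stand.

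1. **The named risk (14.1, 16.1).** Anaphylactic reaction, rare and primarily intravenous. Neither section says what to do about a person who has had one.
2. **The exposure (18.2).** Oral: 3 capsules × 500 mg × 2 per day = 3000 mg per day, for 7 weeks.
3. **Inclusion criteria (12.5).** Age, alcohol use disorder, beneficiary status. On a previous reaction: 0 of 3.
4. **Exclusion criteria (12.6).** Psychiatric diagnosis, current medication for alcohol use disorder, pregnancy, English fluency, planned pregnancy, alcohol-related hospitalization, seizures or delirium tremens, liver disease, neurocognitive disorder, never enrolled in the clinic. On a previous reaction: 0 of 10. The list has no general item for investigator judgement or medical contraindication.
5. **Phone screen (13.3).** The one broad medical question concerns chronic conditions linked to alcohol. On drug allergy: 0 of 12.
6. **Baseline items (10.1, 10.2).** The content of the physical exam is not described. The medication item, as described, does not cover allergies.
7. **Risk minimization (14.2).** Drug side effects are referred to 16.1, which deals with assessment, grading, reporting and follow-up once dosing has begun.
8. **Contraindications (18.2).** The pointer leads to 14.1 and 16.1, and so back to step 1.

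Now follow a candidate with a known earlier reaction. The phone screen does not ask. The exam may or may not bring it out. If it does, no criterion makes the answer disqualifying, so the physician or prescriber decides case by case. The principal investigator may end participation in the person's best interest, for inability to comply, or for lost eligibility. This person has lost no eligibility, so only the discretionary first ground would normally fit. The notice to outside clinicians comes late: "Participants will be given a business card to give to their provider stating they are in the study" appears in 10.1 after the randomization step.

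**The case against.** The strongest reply is that the key premise is not in the documents. Exclusion is needed only if a past reaction raises the risk from oral NAC, and nothing here says that it does, least of all for a past intravenous reaction. Sections 14.1 and 16.1 list anaphylaxis as a rare side effect, not as a contraindication. This stands. It makes exclusion a cautious default and not the correction of a demonstrated error.

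A second reply is that sensible people stand between the candidate and the first dose: an examining physician, named prescribers, an investigational pharmacy, and a principal investigator with discretion. The study script, assessment descriptions and flowsheets are attachments that we do not have, and the consent pages were removed from the text. A reader might infer that nobody would ask about allergy, or that known reactors would be let in. The documents do not support that inference. They show only that no written rule decides the matter.

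A reader might also infer an internal contradiction from the handling of pregnancy, which has exclusions (one is "Trying to get pregnant in the next 4 months"), a phone question and a baseline test. The comparison does not carry that weight. Section 14.1 says of pregnancy and lactation that "given the limited reports on NAC in pregnant and lactating women, it should not be used in this population in the context of research", and it declares an exclusion. It says nothing of the kind about previous reactors. A stated non-use population and a rare side effect may reasonably be treated differently. Nor is the benchmark clean, since lactation is named there but appears in neither 12.6 nor 13.3.

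Last, 16.1 limits harm after dosing: physician grading of itching and rash, unblinding for severe related events, emergency referral and the pausing rule. These lower the consequence. They do not settle who may be randomized.

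**Conclusion.** The point holds as a minor safety improvement. On the written criteria a person with a known previous allergic or anaphylactic reaction to acetylcysteine is eligible, and keeping that person out rests on undescribed or discretionary steps.

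The probability is low, because the route is oral and the protocol calls the reaction rare and mainly intravenous. The documents give no share of candidates with such a history and no rate of oral reactions, so the expected harm cannot be quantified and no figure for it is offered. The point has no bearing on any estimate, error rate or on the sample size of 50.

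The conclusion rests on the printed lists in 12.5, 12.6 and 13.3 being complete. An allergy question in an unseen attachment would narrow the gap but not close it, because no criterion would act on the answer. The case for change rests on its very low cost against a serious reaction that the protocol itself names.

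**What to change.** Four small changes in one minor amendment:

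- Add to 12.6 the exclusion *previous allergic or anaphylactic reaction to acetylcysteine*.
- Add one matching question to the 13.3 phone screen.
- Have the physician confirm the answer at the existing baseline exam, before randomization.
- List the history in the contraindications field of 18.2.

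If the script or exam form already asks, only the exclusion line and the field entry are needed.

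No visit or procedure is added. The downside is a very rare extra screen failure. Purely as an illustration of that cost, assume that a share p of otherwise eligible people have the history, with p between 0.01% and 1%; the documents support no particular value. Extra screen failures per 50 otherwise enrolled are then 50 × p, from 50 × 0.0001 = 0.005 to 50 × 0.01 = 0.5. That is less than one person even at the top of the assumed range.

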#### 12.5 Inclusion Criteria:

Order Number	Criteria
1	≥ 18 years of age.
2	Meets DSM-V criteria for alcohol use disorder on the SCID-5
3	MHS Healthcare Beneficiary NOTE: While we are recruiting explicitly from the ATS patient population, we do not require that they are currently receiving treatment at ATS. For participants that are not currently in care we will provide them with resources to pursue psychotherapy while engaged in our study as outlined in the interview treatment questions and physical and mental health resource document.

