### **Expected Adverse Events (EAEs)**

The primary EAEs for the study will be potential medication side effects.

Side effects are uncommon and relatively minor. The most frequently reported side effects are nausea, vomiting, and diarrhea. They often occur at identical rates to placebo. Rarely and primarily with intravenous administration, anaphylactic reactions may occur and can consist of rash, pruritus, angioedema, bronchospasm, tachycardia, and blood pressure dysregulation. Finally, given the limited reports on NAC in pregnant and lactating women, it should not be used in this population in the context of research and thus this is an exclusion criteria.

Sources: 1) FDA approved acetylcysteine labels (<https://dailymed.nlm.nih.gov/dailymed/index.cfm>)

To assess them, the study physician will use the Systematic Assessment for Treatment Emergent Events (SAFTEE) interview at each in-person appointment. This includes asking about common symptom indicators as well as an "other" option to record other side effects:

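### The risk sections declare lactating women excluded, but no eligibility criterion, screening question or baseline check carries that exclusion

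*Combined protocol and SAP*

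**What the plan says.** Two places treat lactation as a reason not to give NAC. Section 14.1 (Risks of Harm) refers to the sparse evidence in "pregnant and lactating women, it should not be used in this population in the context of research and thus this is an exclusion criteria". Section 16.1, under Expected Adverse Events, makes the same statement: "given the limited reports on NAC in pregnant and lactating women, it should not be used in this population in the context of research". In section 18.2, the drug-details entry for contraindications gives no content of its own and points to 14.1 and 16.1, so these two sections are the protocol's contraindication statement.

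The sections that decide who is enrolled cover pregnancy only:

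- Section 12.6 (Exclusion Criteria) has two reproductive items: pregnancy, and "Trying to get pregnant in the next 4 months".
- Section 13.3 (pre-screening) has one female-specific question: "Female only: Are you pregnant or trying to get pregnant sometime in the next 4 months".
- Section 10.1, Baseline Visit, adds that "female participants will undergo a pregnancy screen using a pregnancy test kit". Section 10.2 identifies the kit as a urine hCG test.

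**The concern.** The protocol tells the IRB that a group is excluded on safety grounds, but the operative lists do not exclude that group. Research staff screen from 12.6 and 13.3. If they follow both to the letter, they can enrol someone whom 14.1 says should not receive the drug.

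This is a participant-safety matter and has no bearing on the estimates. It also affects oversight. An IRB member reading 14.1 would reasonably take the exclusion to be in force, and a monitor checking enrolments against 12.6 would have no criterion on which to call such an enrolment a deviation.

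**Working it through.** The plan states no figure to reproduce. The check follows one hypothetical woman through every eligibility and safety step in the text. She is breastfeeding, not pregnant, not trying to conceive and otherwise eligible.

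| Step | Section | Items touching lactation | Result for her |
|---|---|---|---|
| Inclusion criteria | 12.5 | 0 of 3 (age, AUD on the SCID-5, beneficiary status) | Meets all |
| Exclusion criteria | 12.6 | 0 of 10 | Meets none |
| Phone screen | 13.3 | 0 of 12 | Answers no to question 11 and is booked for baseline |
| Physical exam | 10.1, 10.2 | Content not described; no lactation question specified | No stated reason to stop |
| Pregnancy test | 10.1, 10.2 | hCG only | Negative |
| Baseline questionnaires and interviews | 10.2 | None | Proceeds |
| Randomisation | 10.1, 11.4 | Same visit; 25 per arm | Allocated |
| Weeks 1, 3 and 5 | 10.1 | Women are asked only about a change in pregnancy status | Continues |
| Risk-minimisation measures | 14.2 | None | Nothing triggered |

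Across the documents, lactation is named in two places, 14.1 and 16.1, and in no eligibility or screening text.

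The contrast with pregnancy is informative. The same sentence in 14.1 names both conditions. Pregnancy was turned into a criterion (12.6), a phone question (13.3), a baseline test and repeat questions at weeks 1, 3 and 5 (10.1). Lactation was turned into none of these.

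Later steps do not reliably close the gap. The assessment schedule in 10.2 shows the eligibility check once, at the phone screen, and that call does not ask. The monitoring plan in 15.1 lets the principal investigator end participation when someone no longer meets the eligibility criteria, but the 12.6 list gives no lactation criterion to apply.

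If she were enrolled:

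- Chance of NAC: 25 / (25 + 25) = 1 in 2.
- Planned course, from section 18.2 (three 500 mg capsules twice a day) and the seven-week treatment period: 3 × 2 = 6 capsules a day; 6 × 49 days = 294 capsules; 294 × 0.5 g = 147 g.

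These figures describe what one such participant would be assigned. They measure neither how often this would happen nor how harmful it would be. The documents give no number of lactating women among the clinic's patients.

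**The case against.** The best defence is that this is an omission and not a conflict. No section permits lactating women to enrol. Sections 14.1 and 16.1 are current protocol text and call the matter an exclusion criterion, and the contraindications entry in 18.2 sends prescribers and pharmacy there. Read as a whole, the protocol has one rule that was not copied into its list. A physician also examines every participant before randomisation. The detailed script, the assessment attachment and the session checklists were not available, and consent pages were removed from the text, so a breastfeeding question or statement may exist in one of them. Finally, the stated reason is limited reports, not a known hazard, and the protocol describes side effects as uncommon and minor.

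Part of this stands. The sponsor's intent to exclude is fairly clear, the unseen attachments limit what can be claimed about actual practice, and nothing in the documents shows that serious harm is likely.

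The main point survives. Even if 14.1 sets the exclusion by itself, no described step applies it. The entry in 18.2 only points back and adds no screening. The protocol specifies no lactation question at the exam. A question in an attachment would not repair 12.6, which is the list against which eligibility is judged. If the sentence was meant to cover pregnancy alone, then 14.1 and 16.1 misstate the safeguard and still need correcting.

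**Conclusion.** The concern holds. Sections 14.1 and 16.1 assert an exclusion that appears in 0 of 10 exclusion criteria, 0 of 12 phone-screen questions and no described baseline procedure. Staff who apply the listed criteria as written could randomise a woman the protocol says is excluded. She would have a 1-in-2 chance of the full NAC course.

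The number of women affected is unknown and, with 50 participants, may be zero. The conclusion assumes that staff screen from 12.6 and 13.3, and it is limited to the text available: a lactation question in an unseen attachment would lower the practical risk but leave the inconsistency. It should be corrected before anyone is enrolled under this text, because it concerns who may be given study drug and costs very little to put right.

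**What to change.** Make the risk sections and the operative text agree, in one of two ways:

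1. If the exclusion is intended, add a lactation row to 12.6, extend phone-screen question 11 in 13.3 to ask about it, and have the physician confirm it at the baseline visit (10.1) before randomisation. Bring the script and session checklists into line.
2. If it is not intended, correct the sentence in both 14.1 and 16.1, so that the IRB is not told of a safeguard that is not applied. The contraindications entry in 18.2 then follows, since it refers to those sections.

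The choice between these, and the exact clinical wording, belongs to the sponsor's clinicians.

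The cost is a short protocol amendment: one table row, a few words in one question and one line in the baseline procedure, or a corrected sentence in two places. Sample size, randomisation and analysis do not change. The effect on recruitment should be small, although the documents give no count from which to calculate it.
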